### **3.6 Post-Study Drug Study Follow up**

In this study, overall survival is the primary endpoint. Post-study follow-up is of critical importance and is essential to preserving subject safety and the integrity of the study. Subjects who discontinue study drug must continue to be followed for collection of outcome and/or survival follow-up data as required and in line with [Section 5](#) until death or the conclusion of the study. Subjects who discontinue study drug for reasons other than disease progression will continue to have tumor assessments (if clinically feasible) according to the schedule in [Table 5.1-2](#) and [Table 5.1-3](#) until progression.

BMS may request that survival data be collected on all treated subjects outside of the protocol window ([Table 5.1-4](#)). At the time of this request, each subject will be contacted to determine their survival status unless the subject has withdrawn consent for all contacts or is lost to follow up.

#### **3.6.1 Withdrawal of Consent**

Subjects who request to discontinue study drug will remain in the study and must continue to be followed for protocol specified follow-up procedures. The only exception to this is when a subject specifically withdraws consent for any further contact with him/her or persons previously authorized by subject to provide this information. Subjects should notify the investigator of the decision to withdraw consent from future follow-up **in writing**, whenever possible. The withdrawal of consent should be explained in detail in the medical records by the investigator, as to whether the withdrawal is from further treatment with study drug only or also from study procedures and/or post treatment study follow-up, and entered on the appropriate CRF page. In the event that vital status (whether the subject is alive or dead) is being measured, publicly available information should be used to determine vital status only as appropriately directed in accordance with local law.

#### **3.6.2 Lost to Follow-Up**

All reasonable efforts must be made to locate subjects to determine and report their ongoing status. This includes follow-up with persons authorized by the subject as noted above. Lost to follow-up is defined by the inability to reach the subject after a minimum of three documented phone calls, faxes, or emails as well as lack of response by subject to one registered mail letter. All attempts should be documented in the subject's medical records. If it is determined that the subject has died, the site will use permissible local methods to obtain the date and cause of death.

If investigator's use of third-party representative to assist in the follow-up portion of the study has been included in the subject's informed consent, then the investigator may use a Sponsor-retained third-party representative to assist site staff with obtaining subject's contact information or other public vital status data necessary to complete the follow-up portion of the study. The site staff and representative will consult publicly available sources, such as public health registries and databases, in order to obtain updated contact information. If after all attempts, the subject remains

lost to follow-up, then the last known alive date as determined by the investigator should be reported and documented in the subject's medical records.

#### **4 STUDY DRUG**

Study drug includes both Investigational [Medicinal] Product (IP/IMP) and Non-investigational [Medicinal] Product (Non-IP/Non-IMP) and can consist of the following:

**Table 4-1: Study Drugs for CA209459:**

Product Description / Class and Dosage Form	Potency	IP/Non-IMP	Blinded or Open Label	Packaging/ Appearance	Storage Conditions (per label)
Nivolumab Solution for Injection a	100 mg (10 mg/mL)	IP	Open Label	10 mL per vial (5 or 10 vials/carton) Clear to opalescent colorless to pale yellow liquid. May contain particles	2 to 8° C. Protect from light and freezing
Sorafenib Tablets b	200 mg	IP	Open Label	Wallet/blister card containing 28 film-coated tablets. Red and round with the Bayer cross on one side and “200” on the other side.	Store at 15°C to 25°C

a May be labeled as either BMS-936558-01 or Nivolumab

b These products may be obtained by the investigational sites as local commercial product in certain countries if allowed by local regulations. In these cases, products may be a different pack size/potency than listed in the table. These products should be prepared/stored/administered in accordance with the package insert or summary of product characteristics (SmPC)

#### **4.1 Investigational Product**

An investigational product, also known as investigational medicinal product in some regions, is defined a pharmaceutical form of an active substance or placebo being tested or used as a reference in a clinical study, including products already with a marketing authorization but used or assembled (formulated or packaged) differently than the authorized form, or used for an unauthorized indication, or when used to gain further information about the authorized form.

The investigational product should be stored in a secure area according to local regulations. It is the responsibility of the investigator to ensure that investigational product is only dispensed to study subjects. The investigational product must be dispensed only from official study sites by authorized personnel according to local regulations.

In this protocol, investigational products are: BMS-936558 (nivolumab) and Sorafenib.

#### **4.2 Non-investigational Product**

Other medications used as support or escape medication for preventative, diagnostic, or therapeutic reasons, as components of the standard of care for a given diagnosis, may be considered as non-investigational products.

Infusion-related supplies (eg, IV bags, in-line filters, 0.9% sodium chloride injection, 5% dextrose injection) will not be supplied by the sponsor and should be purchased locally if permitted by local regulations.

Please refer to the current version of the Investigator Brochure and/or pharmacy reference sheets for complete storage, handling, dispensing, and infusion information for BMS-936558 (nivolumab).

#### **4.3 Storage and Dispensing**

The product storage manager should ensure that the study drug is stored in accordance with the environmental conditions (temperature, light, and humidity) as determined by BMS. If concerns regarding the quality or appearance of the study drug arise, the study drug should not be dispensed and contact BMS immediately.

Study drug not supplied by BMS will be stored in accordance with the package insert.

Investigational product documentation (whether supplied by BMS or not) must be maintained that includes all processes required to ensure drug is accurately administered. This includes documentation of drug storage, administration and, as applicable, storage temperatures, reconstitution, and use of required processes (eg, required diluents, administration sets).

##### **4.3.1 Nivolumab (BMS-936558)**

Please refer to the current version of the Investigator Brochure and/or pharmacy reference sheets for complete storage, handling, dispensing, and infusion information for BMS-936558 (nivolumab).

BMS-936558 (nivolumab) is to be administered as an IV infusion over 30 minutes. At the end of the infusion, flush the line with a sufficient quantity of dextrose or normal saline.

### **4.3.2 Sorafenib**

Please refer to the SmPC for complete storage, handling and dispensing information for sorafenib.

## **4.4 Method of Assigning Subject Identification**

CA209459 is a randomized, open-label study. After the subject's initial eligibility is established and informed consent has been obtained, the subject must be enrolled into the study by calling an interactive voice response system (IVRS) to obtain the subject number. Every subject that signs the informed consent form must be assigned a subject number in IVRS. Specific instructions for using IVRS will be provided to the investigational site in a separate document.

The investigator or designee will register the subject for enrollment by following the enrollment procedures established by BMS. The following information is required for enrollment:

- Date that informed consent was obtained
- Date of birth
- Gender at birth
- Viral status at time of enrollment, if known

Once enrolled in IVRS, enrolled subjects that have met all eligibility criteria will be ready to be randomized through IVRS. The following information is required for site entry in the IVRS prior to subject randomization:

- Subject number
- Date of birth
- Vascular invasion and/or extrahepatic spread (present or absent)

Additional information will be automatically transferred to the IVRS by the Central Lab and must be available prior to subject randomization:

- Etiology (HCV vs non-HCV)
- Confirmation of tumor tissue sample receipt and acceptability at Central Laboratory

Subjects meeting all eligibility criteria will be randomized in a 1:1 ratio to nivolumab or sorafenib, stratified by the following factors:

- Etiology - HCV vs non-HCV
- Vascular invasion and/or extrahepatic spread (present or absent)
- Geography (Asia vs. Non-Asia)

The randomization procedures will be carried out via permuted blocks within each stratum. The exact procedures for using the IVRS will be detailed in the IVRS manual.

## 4.5 Selection and Timing of Dose for Each Subject

Dosing schedules for both arms are detailed in Table 4.5-1. The first dose of study drug is to be administered within 3 days of randomization. Treatment dosing details are described separately for each Arm below. All subjects will be monitored continuously for AEs while on study treatment. Treatment modifications (eg, dose delay, reduction, or discontinuation) will be based on specific laboratory and adverse event criteria, as described in Sections 4.5.1 and 4.5.3.

**Table 4.5-1: Selection and Timing of Dose for Each Subject**

Drug	Dose	Frequency of administration	Route of administration	Duration
Nivolumab	240 mg	Every 2 weeks	30 minute intravenous (IV) administration	Until progression, unacceptable toxicity, or discontinuation from study
Sorafenib	400 mg (2 x 200 mg tablets)	Twice daily (BID)	PO	Until progression, unacceptable toxicity, or discontinuation from study

### 4.5.1 Nivolumab Dosing

#### 4.5.1.1 Nivolumab Dose and Schedule

Subjects randomized to nivolumab will receive treatment with nivolumab at a dose of 240 mg as a 30-minute IV infusion, on Day 1 of each treatment cycle every 2 weeks, until progression, unacceptable toxicity, withdrawal of consent, or study end, whichever occurs first.

Subjects may be dosed no less than 12 days between doses. Subjects may be dosed up to 3 days after the scheduled date if necessary. A dose given more than 3 days after the intended dose date will be considered a delay. Subsequent dosing should be based on the actual date of administration of the previous dose of drug.

#### 4.5.1.2 Dose Modifications for Nivolumab

No dose modifications for nivolumab are allowed.

#### 4.5.1.3 Dose Delay Criteria for Nivolumab

Nivolumab administration should be delayed for the following:

- Any Grade  $\geq$  2 non-skin drug-related adverse event, with the following exceptions:
  - Grade 2 drug-related fatigue or laboratory abnormalities do not require a treatment delay
- Any Grade 3 skin drug-related adverse event
- Any Grade 3 drug-related laboratory abnormality with the following exceptions:

- Grade 3 amylase or lipase abnormalities that are not associated with symptoms or clinical manifestations of pancreatitis do not require a dose delay.
- Dose delay for changes in AST or ALT as follows:
  - If a subject has a baseline AST or ALT that is within normal limits, delay dosing for drug-related Grade  $\geq 2$  toxicity (2 grade shift)
  - If a subject has baseline AST or ALT within the Grade 1 toxicity range, delay dosing for drug-related Grade  $\geq 3$  toxicity (2 grade shift)
  - If a subject has baseline AST or ALT within the Grade 2 toxicity range, delay dosing for a two-fold drug-related increase in AST or ALT or for AST or ALT values 8x ULN (whichever is lower).
- Any adverse event, laboratory abnormality, or intercurrent illness which, in the judgment of the investigator, warrants delaying the dose of study medication.

Subjects who require delay of nivolumab should be re-evaluated weekly or more frequently if clinically indicated. It is recommended to monitor elevations in AST or ALT approximately every 3 days till levels peak or begin to decline. Nivolumab dosing can be resumed when re-treatment criteria are met (Section 4.5.1.4).

Tumor assessments for all subjects should continue as per protocol even if dosing is delayed.

#### **4.5.1.4 Criteria to Resume Dosing for Nivolumab**

Subjects may resume treatment with study drug when the drug-related AE(s) resolve to Grade  $\leq 1$  or baseline value, with the following exceptions:

- Subjects may resume treatment in the presence of Grade 2 fatigue.
- Subjects who have not experienced a Grade 3 drug-related skin AE may resume treatment in the presence of Grade 2 skin toxicity.
- Subjects with baseline Grade 1 AST, ALT, or total bilirubin who require dose delays for reasons other than a drug-related hepatic event may resume treatment in the presence of Grade 2 AST, ALT, or total bilirubin.
- Subjects who require dose delays for drug-related elevations in AST, ALT, or total bilirubin may resume treatment when these values have returned to their baseline CTCAE Grade or normal, provided the criteria for permanent discontinuation are not met ([Section 4.5.1.5](#)).
- Drug-related pulmonary toxicity, diarrhea, or colitis, must have resolved to baseline before treatment is resumed.
- Drug-related endocrinopathies adequately controlled with only physiologic hormone replacement may resume treatment.

If the criteria to resume treatment are met, the subject should restart treatment at the next scheduled timepoint per protocol. If treatment is delayed  $> 6$  weeks from the last dose, the subject must be permanently discontinued from study therapy, except as specified in [Section 4.5.1.5](#) and [Section 4.5.1.6](#). Please see also [Appendix 5](#) (Algorithms for Management of Side Effects) for

guidance on appropriate management and follow-up of adverse events. For hepatic AE management, see [Section 4.5.2.2](#).

#### **4.5.1.5 Treatment Discontinuation Criteria for Nivolumab**

Treatment with nivolumab should be permanently discontinued for the following

- Any Grade 2 drug-related uveitis or eye pain or blurred vision that does not respond to topical therapy and does not improve to Grade 1 severity within the re-treatment period OR requires systemic treatment.
- Any Grade 3 non-skin, drug-related adverse event lasting > 7 days or recurs, with the following exceptions:
  - Grade 3 drug-related uveitis, pneumonitis, bronchospasm, neurologic toxicity, myocarditis, hypersensitivity reaction, or infusion reaction of any duration requires discontinuation. Adrenal insufficiency requires discontinuation regardless of control with hormone replacement.
  - Grade 3 drug-related endocrinopathies adequately controlled with only physiologic hormone replacement do not require discontinuation
  - Grade 3 drug-related laboratory abnormalities do not require treatment discontinuation except:
    - ◆ Grade 3 drug-related thrombocytopenia > 7 days or associated with bleeding requires discontinuation
- Hepatotoxicity as evidenced by the following:
  - AST or ALT > 10 x ULN for > 2 weeks,
  - AST or ALT > 15 x ULN irrespective of duration,
  - Total bilirubin > 5 x ULN for those with normal total bilirubin at entry or > 8 x ULN for subjects with elevated bilirubin at study entry, irrespective of duration.
- Any Grade 4 drug-related adverse event or laboratory abnormality, except for the following events which do not require discontinuation:
  - Grade 4 neutropenia < 7 days
  - Grade 4 lymphopenia or leukopenia
  - Isolated Grade 4 amylase or lipase abnormalities that are not associated with symptoms or clinical manifestations of pancreatitis. The BMS Medical Monitor should be consulted for Grade 4 amylase or lipase abnormalities.
  - Isolated Grade 4 electrolyte imbalances or abnormalities that are not associated with clinical sequelae and are corrected with supplementation and appropriate management within 72 hours of their onset.
  - Grade 4 drug-related endocrinopathies adequately controlled with only physiologic hormone replacement do not require discontinuation.
- Any dosing delay lasting > 6 weeks with the following exceptions:
  - Dosing delays to allow for prolonged steroid tapers to manage drug-related adverse events are allowed. Prior to re-initiating treatment in a subject with a dosing delay lasting > 6 weeks, the BMS medical monitor must be consulted. Tumor assessments should continue

as per protocol even if dosing is delayed. Periodic study visits to assess safety and laboratory studies should also continue every 6 weeks or more frequently if clinically indicated during such dosing delays.

- Dosing delays lasting > 6 weeks from the previous dose that occur for non-drug-related reasons may be allowed if approved by the BMS medical monitor. Prior to re-initiating treatment in a subject with a dosing delay lasting > 6 weeks, the BMS Medical Monitor must be consulted. Tumor assessments should continue as per protocol even if dosing is delayed. Periodic study visits to assess safety and laboratory studies should also continue every 6 weeks or more frequently if clinically indicated during such dosing delays.
- Any adverse event, laboratory abnormality, or intercurrent illness which, in the judgment of the Investigator, presents a substantial clinical risk to the subject with continued nivolumab dosing.
- Investigator assessed disease progression according to RECIST 1.1 (unless subject meets criteria as specified in Section 4.5.1.6)

Tumor assessments for all subjects should continue as per protocol even if study drug dosing is discontinued.

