### **3.5 Discontinuation of Subjects following any Treatment with Study Drug**

Subjects MUST discontinue investigational product (and non-investigational product at the discretion of the investigator) for any of the following reasons:

- Subject's request to stop study treatment
- Any clinical adverse event (AE), laboratory abnormality or intercurrent illness which, in the opinion of the investigator, indicates that continued participation in the study is not in the best interest of the subject
- Termination of the study by Bristol-Myers Squibb (BMS)
- Loss of ability to freely provide consent through imprisonment or involuntarily incarceration for treatment of either a psychiatric or physical (eg, infectious disease) illness
- Specific criteria for discontinuation of study drugs are outlined for nivolumab in [Section 4.5.1.5](#) and for sorafenib in [Section 4.5.3.3](#).
- Disease progression unless the subject is eligible for treatment beyond progression ([Section 4.5.1.6](#) for nivolumab and [Section 4.5.3.4](#) for sorafenib)

In the case of pregnancy, the investigator must immediately notify the BMS Medical Monitor/designee of this event. In most cases, the study drug will be permanently discontinued in an appropriate manner. If the investigator determines a possible favorable benefit/risk ratio that warrants continuation of study drug a discussion between the investigator and the BMS Medical Monitor/designee must occur.

All subjects who discontinue study drug should comply with protocol specified follow-up procedures as outlined in [Section 5](#). The only exception to this requirement is when a subject withdraws consent for all study procedures including post-treatment study follow-up or loses the ability to consent freely (ie, is imprisoned or involuntarily incarcerated for the treatment of either a psychiatric or physical illness).

If study drug is discontinued prior to the subject's completion of the study, the reason for the discontinuation must be documented in the subject's medical records and entered on the appropriate case report form (CRF) page.

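### Protocol 4.5.1.5 stops nivolumab for adrenal insufficiency even when hormone-controlled, but its Grade 4 endocrinopathy exception does not exclude adrenal insufficiency (minor safety-wording correction)

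*Protocol*

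**What the plan says.** Protocol Section 4.5.1.5 lists the criteria for permanently stopping nivolumab. One top-level criterion covers Grade 3 non-skin drug-related events that last more than 7 days or recur, followed by a list of exceptions. The first bullet of that list names Grade 3 events that require a stop whatever their duration, and its second sentence reads: "Adrenal insufficiency requires discontinuation regardless of control with hormone replacement". The next bullet lets hormone-controlled Grade 3 endocrinopathies continue.

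A separate top-level criterion follows for Grade 4: "Any Grade 4 drug-related adverse event or laboratory abnormality, except for the following events which do not require discontinuation". The last item in its list is: "Grade 4 drug-related endocrinopathies adequately controlled with only physiologic hormone replacement do not require discontinuation".

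Section 3.5 makes these criteria binding. Its list opens with "Subjects MUST discontinue investigational product" and includes the entry "Specific criteria for discontinuation of study drugs are outlined for nivolumab in" Section 4.5.1.5.

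**The concern.** Adrenal insufficiency is an endocrinopathy treated with hormone replacement. A drug-related Grade 4 case that is well controlled on physiologic replacement therefore falls within the words of both rules. One says stop despite hormone control. The other says that hormone control removes the need to stop. No order of precedence is given.

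At stake is whether a mandatory safety stop is stated clearly at the more severe grade. If it is not, two sites could treat the same event differently while each believes it is following the protocol.

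**Working it through.** There is no figure in the plan to reproduce. The check sets the rules side by side for one case: drug-related adrenal insufficiency, adequately controlled with physiologic replacement only.

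**1. What the adrenal sentence covers.** It names no grade and does not say drug-related, which points to a rule of its own. It also negates the very condition, hormone control, on which the endocrinopathy exceptions rest. But it is the second sentence of a Grade 3 sub-bullet and not a separate criterion.

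**2. Outcome under each reading.**

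| Reading of the adrenal sentence | Controlled Grade 3 | Controlled Grade 4 |
|---|---|---|
| Applies at all grades, as the more specific rule | Stop | Stop, but only if the reader infers that it outranks the Grade 4 exception |
| Limited to its Grade 3 parent criterion | Stop | No stop required |

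The first reading gives a sensible result. The second gives an inverted one, stricter at the lower grade. The second also depends on the bullet levels, which should be confirmed against the formatted protocol.

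**3. Whether nearby text settles it.**
- Section 4.5.1.3 delays dosing for a Grade 2 or higher "non-skin drug-related adverse event, with the following exceptions". That is a delay, not a permanent stop.
- Section 4.5.1.4 states: "Drug-related endocrinopathies adequately controlled with only physiologic hormone replacement may resume treatment". It has no grade limit and no adrenal exclusion. It does not contradict 4.5.1.5, because a permanent discontinuation takes precedence over resumption, but it does not clarify the point either.
- The last part of 4.5.1.5 requires a stop for an event that, "in the judgment of the Investigator, presents a substantial clinical risk to the subject with continued nivolumab dosing". This depends on judgment and is not a fixed stop for adrenal insufficiency.
- Section 4.5.1.4 refers sites to Appendix 5 for adverse event management. That appendix is not in the supplied text, and Section 4.5.2 is redacted, so neither could be checked.

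**4. Whether explicit carve-outs were available to the drafters.** They were used elsewhere. The Grade 3 laboratory exception in 4.5.1.5 goes on to name thrombocytopenia as an event that still requires a stop. The hepatic resumption bullet in 4.5.1.4 is made conditional on the permanent discontinuation criteria not being met. The Grade 4 endocrinopathy exception and the endocrinopathy resumption bullet have no such qualifier.

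**5. Size.** The documents give no rate. As an illustration only, assume that 0.1% to 1% of the approximately 363 nivolumab subjects (Protocol 3.1) have controlled drug-related Grade 4 adrenal insufficiency:
- 363 × 0.001 = 0.36
- 363 × 0.01 = 3.63

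That is roughly 0.4 to 3.6 subjects. Both ends are assumptions, so this range is not a bound.

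**The case against.** The best counter-argument is that 4.5.1.5 is a list of separate triggers. An exception inside the Grade 4 criterion switches off that criterion only. It does not cancel others, such as hepatotoxicity, a delay beyond 6 weeks or investigator judgment. On that view the adrenal sentence is a specific, independent trigger and still requires a stop at Grade 4. The Grade 3 endocrinopathy exception also lacks an adrenal exclusion, yet nobody would doubt that the adrenal sentence governs there. All that is missing is a cross-reference.

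Most of this stands, and it is the likeliest intent. It limits what can be claimed. A reader might infer that the Grade 4 stop fails on any reading, or that the protocol positively allows nivolumab to continue after Grade 4 adrenal insufficiency. The documents do not support either inference, because the more natural reading requires the stop. Nor do they show that sites would be misled, since Appendix 5 may give clear guidance.

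What remains is that precedence at Grade 4 must be inferred. At Grade 3 the adrenal sentence sits in the same list as the exception that it overrides. At Grade 4 it sits under a different criterion, and the exception says without qualification that no stop is required.

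The practical consequences are also limited. Stopping always complies, dosing is already delayed for a Grade 4 event, and the investigator must stop if continuation is judged unsafe.

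**Conclusion.** The point holds as a minor wording defect in a mandatory safety rule. Section 4.5.1.5 does not state that the adrenal stop applies at Grade 4, and its nesting, taken literally, gives a stricter rule at Grade 3 than at Grade 4. The intended rule is probably a stop at both grades.

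Few subjects would be affected, though any count rests on an assumed rate. Efficacy is analysed by randomized arm (Protocol 8.2), so the overall survival analysis, the sample size and the type I error are unchanged. The conclusion concerns the wording of 4.5.1.5 and leaves open what Appendix 5 says.

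A reader might also infer that adrenal insufficiency of any grade and any cause should become a top-level stopping criterion. The documents do not support going that far. Exclusion criterion 2m in Section 3.3.2 allows adrenal replacement doses at entry, and Section 3.4.1.2 allows them during nivolumab treatment. An ungraded rule not limited to drug-related events could therefore catch subjects with pre-existing adrenal insufficiency whom the protocol accommodates.

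**What to change.** 1. In the Grade 4 endocrinopathy exception of 4.5.1.5, insert *except adrenal insufficiency* directly after the word endocrinopathies.
2. Insert the same words in the Grade 3 endocrinopathy exception.
3. In the endocrinopathy resumption bullet of 4.5.1.4, add the condition that the hepatic bullet already carries: resumption only if no permanent discontinuation criterion in 4.5.1.5 is met.
4. Do not create a new ungraded top-level criterion that reaches beyond drug-related events. The sponsor's medical team should set any grade range for the adrenal rule.
5. Check that Appendix 5 agrees.

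The cost is a short amendment and a notice to sites. The clinical downside is that a rare subject with controlled drug-related Grade 4 adrenal insufficiency must stop nivolumab. No statistical analysis changes.
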